### **2.9.3. Vital Signs**

Observed values of vital sign parameters (temperature, SBP/DBP, heart rate, and respiration rate) and corresponding changes from baseline (Visit 2/Day 0) will be listed and summarized by descriptive statistics (n, mean, median, standard deviation, minimum and maximum) by visit.

A clinically significant change from baseline (Visit 2/Day 0) will be recorded as a TEAE if deemed appropriate by the Investigator.

### **2.9.4. Physical Examination**

Individual physical examination findings will be listed by visit. A clinically significant change from Baseline (Visit 2/Day 0) will be recorded as a TEAE if deemed appropriate by the Investigator.

Results of the physical examination will be listed and summarized in frequency tables by body system.

A clinically significant change from Screening will be recorded as an AE if deemed appropriate by the Investigator.

### **2.9.5. Electrocardiogram**

Observed values of continuous ECG parameters and corresponding changes Visit 2/Day 0 will be summarized by descriptive statistics (n, mean, median, standard deviation, minimum and maximum). Results of ECG measurements will be summarized in frequency tables by visit.

A clinically significant change from baseline (Visit 2/Day 0) will be recorded as an AE if deemed appropriate by the Investigator.

Fridericia's formula will be used to derive the QT correction, QTcF parameter. QTcF is defined as the QT interval divided by the cubed root of the RR interval ( $QTcF = QT / \sqrt[3]{RR}$ ).

## **2.10. Exploratory Efficacy Analyses**

### **2.10.1. Investigator Global Assessment: Necrobiosis Lipoidica (IGA:NL)**

The IGA:NL will be assessed at every visit the patient visits the clinic (i.e. excluding Visit 3 and 4). The IGA:NL will be used to assess the presence and severity of necrobiosis lesions. The two scales that will be determined are Activity and Damage. Activity has a 6-point scale (0-5) and Damage a 3-point scale (0-2).

The outcomes from this assessment will be treated as categorical and will be listed and summarized by frequency tables.

The outcomes detailed below will be listed and summarized by descriptive statistics (n, mean, median, standard deviation, minimum and maximum) by visit.

- Proportion of patients with scores of clear or almost clear (0 or 1) of the reference lesion on the Activity Scale at Months 1, 2, 3, 4, 5, 6, 9, and 12.
- Proportion of patients with  $\geq 1$ -point decrease in Activity score of the reference lesion at Months 1, 2, 3, 4, 5, 6, 9, and 12.
- Proportion of patients with  $\geq 2$ -point decrease in Activity score of the reference lesion at Months 1, 2, 3, 4, 5, 6, 9, and 12.
- Time to obtaining scores of clear or almost clear (0 or 1) of reference lesion on the IGA:NL Activity scale.

Proportion of subjects with  $\geq 1$  point decrease or  $\geq 2$  decrease in Activity score will be determined from the baseline Visit 2/Day 0.

Time to obtaining scores of clear or almost clear (0 or 1) will be defined as the difference between the date when this outcome of interest is determined and the date of first study drug exposure.

### **2.10.2.Necrobiosis Lipoidica Color and Ulcer Scale (NLCUS)**

The NLCUS will be assessed starting at Visit 2/Day 0 and at every clinic visit through Month 12. The NLCUS will be used to assess the color and ulcer of necrobiosis lesions. The three scales that will be determined are Color/Inflammation, Induration, and Ulcer. Color/Inflammation has a 5-point scale (0-4), Induration a 5-point scale (0-4), and Ulcer a 3-point scale (0-2).

The outcomes from this assessment will be treated as categorical and will be listed and summarized by frequency tables.

The outcomes detailed below will be listed and summarized by descriptive statistics (n, mean, median, standard deviation, minimum and maximum) by visit.

- Proportion of patients with  $\geq$  1-point decrease in the Color score of the reference lesion at Months 1, 2, 3, 4, 5, 6, 9, and 12.
- Among patients with ulceration at Baseline only: Proportion of patients with  $\geq$  1-point decrease in the Ulcer score on the Color and Ulcer Scale (NLCUS) of the reference lesion at Months 1, 2, 3, 4, 5, 6, 9, and 12.

### **2.10.3.Physician Global Assessment (PGA)**

The PGA will be assessed using a 10 cm VAS ranging from “none” to “extreme activity”. The distance marked in centimeters from “none” to “extreme activity” and the change from baseline (Visit 2/Day 0) will be listed and summarized by descriptive statistics (n, mean, median, standard deviation, minimum and maximum) by visit.

### **2.10.4.Patient Global Assessment (PtGA)**

The PtGA will be assessed using a 10 cm VAS ranging from “not at all” to “very severe”. The distance marked in centimeters from “not at all” to “very severe” and the change from baseline (Visit 2/Day 0) will be listed and summarized by descriptive statistics (n, mean, median, standard deviation, minimum and maximum) by visit.

### **2.10.5.Lesion/ulcer surface area**

Surface area of the lesions(s)/ulcer will be measured by the Investigator and by photography. Continuous outcomes, separately for those measured by the Investigator and by photography, and changes from baseline (Visit 2/Day 0), will be listed and summarized by descriptive statistics (n, mean, median, standard deviation, minimum and maximum) by visit.

The outcomes detailed below will be listed and summarized by descriptive statistics (n, mean, median, standard deviation, minimum and maximum) by visit.

- Percent change from Baseline in reference lesion surface area of inflammation/erythema based on Investigator measurement at Months 1, 2, 3, 4, 5, 6, 9, and 12.
- Percent change from Baseline in total lesion(s) surface area of inflammation/erythema based on Investigator measurement at Months 1, 2, 3, 4, 5, 6, 9, and 12.

- Percent change from Baseline in reference lesion surface area of inflammation/erythema based on photograph at Months 1, 2, 3, 4, 5, 6, 9, and 12.

The outcomes detailed below will be listed and summarized by descriptive statistics (n, mean, median, standard deviation, minimum and maximum) by visit, for patients with ulceration at Baseline only.

- Percent change from Baseline in reference ulcer surface area based on Investigator measurement at Months 1, 2, 3, 4, 5, 6, 9, and 12.
- Percent change from Baseline in total ulcer surface area based on Investigator measurement at Months 1, 2, 3, 4, 5, 6, 9, and 12.
- Percent change from Baseline in reference ulcer surface area based on photograph at Months 1, 2, 3, 4, 5, 6, 9, and 12.

#### **2.10.6.Dermatology Life Quality Index (DLQI)**

The DLQI consists of 10 items and covers six sub-scales including: symptoms and feelings, daily activities, leisure, work and school, personal relationships, and treatment. Scores range from 0 to 30 with higher scores indicating poorer health related quality of life (HRQL).

Each question is scored on a four-point Likert scale (0-3) where the score of 0 can represent one of three possible scenarios:

- Score of 0 can mean “Not at all”, “Not relevant”, or “Question unanswered”
- Score of 1 means “A little”
- Score of 2 means “A lot”
- Score of 3 means “Very much”

The DLQI is administered starting at Visit 2/Day 0 and at every clinic visit until Month 12. Total and sub-scale specific continuous outcomes, and the change from baseline (Visit 2/Day 0), will be listed and summarized by descriptive statistics (n, mean, median, standard deviation, minimum and maximum) by visit.

The six sub-scales include the following items and have the noted maximum score

- Symptoms and feelings includes Questions 1 and 2 with a maximum score of 6
- Daily activities includes Questions 3 and 4 with a maximum score of 6
- Leisure includes Questions 5 and 6 with a maximum score of 6
- Work and school includes Question 7 with a maximum score of 3
- Personal relationships includes Questions 8 and 9 with a maximum score of 6
- Treatment includes Question 10 with a maximum score of 3

#### **2.10.7.Skindex-29**

The Skindex-29 includes 29-items with 3 domains: Symptoms, Emotions and Functioning. Each domain is scored from 0 to 100 with higher scores indicating a lower quality of life and a higher impact of the skin disease. Scoring is based on the Skindex-29 documentation and is done as follows:

- Never = 0
- Rarely = 25
- Sometimes = 50
- Often = 75
- All the time = 100

The Skindex-29 is administered starting at Visit 2/Day 0 and at every clinic visit until Month 12. Total and domain specific continuous outcomes, and the change from baseline (Visit 2/Day 0), will be listed and summarized by descriptive statistics (n, mean, median, standard deviation, minimum and maximum) by visit

The three domains include the following items

- Emotions includes Questions (10) 3, 6, 9, 12, 13, 15, 21, 23, 26, and 28
- Symptoms includes Questions (7) 1, 7, 10, 16, 19, 24, and 27
- Functioning includes Questions (12) 2, 4, 5, 8, 11, 14, 17, 20, 22, 25, 29, and 30

## 2.10.8. Variables in Ulcerated Patients

### Closure of Reference Ulcer

Closure of reference ulcer is defined as skin re-epithelialization without drainage or dressing requirements confirmed at two consecutive study visits 2 weeks apart. Time to complete wound closer will be defined as the difference between the date when wound closure is determined and the date of first dose. Time to closure will be listed and summarized by descriptive statistics (n, mean, median, standard deviation, minimum and maximum).

Continuous outcomes for ulcers that do not close will be included in the listing output but will be excluded from the summary table output.

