### Ulcer volume

Ulcer volume will be assessed using a 3D-imaging system. Data for ulcer volume will be provided to Integrium by an external vendor. Continuous outcome for volume and changes from baseline (Visit 2/Day 0) will be listed and summarized by descriptive statistics (n, mean, median, standard deviation, minimum and maximum).

The outcomes detailed below will be listed and summarized by descriptive statistics (n, mean, median, standard deviation, minimum and maximum) by visit.

- Incidence of new ulceration (defined as a site with no previous ulceration) at Months 1, 2, 3, 4, 5, 6, 9, and 12.
- Time to new ulceration defined as the difference between the date the new ulceration is reported and the date of first dose administration.

The outcomes detailed below will be listed and summarized by descriptive statistics (n, mean, median, standard deviation, minimum and maximum) by visit, separately for patients with ulceration at Baseline only.

- Incidence of complete wound closure of reference ulcer (defined as skin re-epithelialization without draining or dressing requirements confirmed at two consecutive study visits at least 2 weeks apart) at Months 2, 3, 4, 5, 6, 9, and 12.
- Time to complete wound closure of reference ulcer.
- Incidence of recurrence of reference ulcer after complete wound closure at Months 3, 4, 5, 6, 9, and 12.
- Time to recurrence of reference ulcer after complete wound closure.
- Change from Baseline in reference ulcer volume based on 3D scanning at Months 1, 2, 3, 4, 5, 6, 9, and 12.

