## **2.12. Other Analyses**

No other analyses are planned.

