## **2.14. Handling Missing Data**

Listings will be provided for all data. Descriptive statistics will be provided for all planned visits as provided on the Case Report Forms (CRFs). No imputations for missing data will be used in calculations.

Visit windows will not be used in this study. Likewise, unscheduled visits will not be reassigned a visit number based on the visit date.

Dates related to the medications will be imputed using the rules below in an effort to categorize them properly into the summary tables.

Imputing partial or missing start dates:

- If the year is unknown, then the start date will not be imputed. The date will remain missing.
- If the month is unknown, impute the month as January.
- If the day is unknown, impute the day as '01'.

Impute partial or missing stop dates:

- If the year is unknown, then the stop date will not be imputed. The date will remain missing.
- If the month is unknown, impute the month as December.
- If the day is unknown, impute the day to be the last day of the month.

If an imputed stop date is greater than the date of study completion/discontinuation date of the study, then the imputed stop date will be set equal to the date of completion/discontinuation date.

The imputed dates will be stored in the analysis datasets along with the original dates as recorded by the sites.

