## 4.3. Post-text Figures Tables of Contents

There are no figures planned for this study.

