## 4.4. Table Shells

The table shells can be found in a separate file. The following number of decimal places will be used when presenting summary statistics:

- N to 0 decimal places
- Minimum and maximum to the same number of decimal places as recorded in the raw data.
- Means and medians, and confidence intervals to 1 more decimal place than is recorded in the raw data. Standard deviations to 2 more decimal places than is recorded in the raw data.
- Percentages to 1 decimal place.

The precision may be changed for individual endpoints as needed.

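### Time to ulcer closure is summarised over closed ulcers only, and the other three time endpoints become event-only by implication; read as times for all patients, they are too short unless nearly all have the event

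*SAP*

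**What the plan says.** Four exploratory endpoints are times to an event.

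- **Closure of the reference ulcer** (SAP 2.10.8, Closure of Reference Ulcer): date of closure minus date of first dose, summarised by n, mean, median, SD, minimum and maximum. The SAP then adds: "Continuous outcomes for ulcers that do not close will be included in the listing output but will be excluded from the summary table output".
- **IGA:NL Activity 0 or 1** (SAP 2.10.1): "Time to obtaining scores of clear or almost clear (0 or 1) will be defined as the difference between the date when this outcome" is determined and the date of first exposure, with the same descriptive statistics.
- **New ulceration** (SAP 2.10.8, under Ulcer volume): "Time to new ulceration defined as the difference between the date the new ulceration is reported and the date of first dose administration".
- **Recurrence** (same place): listed only as "Time to recurrence of reference ulcer after complete wound closure", without a formula or a time origin.

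SAP 2.14 states: "No imputations for missing data will be used in calculations". SAP 2.12 states: "No other analyses are planned". SAP 4.3 states: "There are no figures planned for this study". Neither document gives a censoring rule or a Kaplan-Meier estimate. The SAP does plan closure, recurrence and new-ulceration incidence by visit (2.10.8), the proportion with IGA:NL 0 or 1 by visit (2.10.1), and full listings.

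**The concern.** A mean or median taken only over patients who had the event describes those patients. It cannot exceed the length of follow-up, however few patients respond. A patient whose ulcer is still open at Month 12 carries information that closure is slow, and the closure rule removes that information from the table. The other three endpoints lose it because a patient without an event date has no value.

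Protocol 9.1 and SAP 1.2 say the study is meant to inform the design of later studies. A planner who took a median time to closure or clearing from these tables as a time for all patients would use too short a figure. The direction is not the same for every endpoint. Short times to closure and clearing look favourable; short times to new ulceration and recurrence look unfavourable.

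**Working it through.** The documents give no expected event rate, time or sample size calculation, so there is no figure of theirs to reproduce. The event rates below are assumptions, shown as a range.

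**Inputs from the documents.** Clinic visits at Days 28, 60, 90, 120, 150, 180, 270 and 360 (Protocol Table 2); 3 to 6 patients with ulcers among about 12 (Protocol 9.3); closure confirmed at two consecutive visits (SAP 2.10.8).

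**Worked example.** Two of six ulcers are confirmed closed at Days 60 and 90; four stay open.
- Event-only: mean = median = (60 + 90)/2 = 75 days.
- Kaplan-Meier: 5/6 = 0.83 still open after Day 60; 0.83 × 4/5 = 0.67 after Day 90. The curve never falls to 0.50, so the median is not reached.

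**Closure on the visit grid.** Assume a constant hazard λ. Closure persists, is first seen at the next visit and is dated at the visit after that. For confirmed closure by Day 360 it must be present by Day 270, so with a share p confirmed, λ = −ln(1 − p)/270. The share dated by a given visit is 1 − exp(−λ × day of the preceding visit).

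For p = 0.70: λ = 1.2040/270 = 0.00446. Cumulative shares dated by Days 60, 90, 120, 150, 180, 270 and 360 are 0.117, 0.235, 0.331, 0.414, 0.488, 0.552 and 0.700.
- Event-only median: first visit at or above 0.70/2 = 0.35, which is Day 150.
- Kaplan-Meier median: first visit at or above 0.50, which is Day 270.

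| Closing by Day 360 | Event-only mean | Event-only median | Kaplan-Meier median |
|---|---|---|---|
| 10% | 214 | 180 | not reached |
| 30% | 206 | 180 | not reached |
| 50% | 195 | 150 | 360 |
| 60% | 188 | 150 | 360 |
| 70% | 179 | 150 | 270 |
| 90% | 150 | 120 | 120 |

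These are large-sample values. The event-only median moves by only 30 days between 10% and 70% closing, so it mainly reflects the visit schedule and the end of follow-up. At 75%, 80% and 85% closing, the two medians differ by one 30-day visit (150/180, 120/150, 120/150).

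**IGA:NL 0 or 1.** No confirmation is needed, so λ = −ln(1 − p)/360. For p = 0.80: λ = 1.6094/360 = 0.00447. Cumulative shares at Days 28, 60, 90, 120, 150 and 180 are 0.118, 0.235, 0.331, 0.415, 0.489 and 0.553. The event-only median (first at or above 0.40) is Day 120; the Kaplan-Meier median is Day 180. The gap is still 60 days at 80%.

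**Check without the visit grid.** With exponential times, the true median is ln 2/λ and the event-only median is −ln(1 − p/2)/λ. Their ratio is −ln(1 − p/2)/ln 2, whatever the length of follow-up: 0.19 at p = 25%, 0.42 at 50%, 0.68 at 75%, 0.86 at 90%, 0.93 at 95%. A bare majority with the event does not remove the shortfall.

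**Separate minor point: dating of closure.** Protocol 14.1.8.1 and SAP 2.10.8 (Closure of Reference Ulcer) put the two confirming visits two weeks apart. The Protocol Synopsis, Protocol 16.2, SAP 1.4.3 and the later list in SAP 2.10.8 say at least two weeks. The smallest gaps between consecutive scheduled clinic visits from Month 1, at the window limits, are 60 − 7 − (28 + 3) = 22 days, then 90 − 7 − (60 + 7) = 16 (the same for the next three), 270 − 10 − (180 + 7) = 73, and 360 − 10 − (270 + 10) = 70. Every scheduled pair meets the second wording and none is exactly two weeks apart. SAP 2.10.8 also does not say whether the first or the confirming visit dates closure.

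**The case against.** Time to closure among ulcers that closed is a legitimate conditional description, and the SAP states its rule openly. It is too short only when read as a time for all patients. The planned n, incidence by visit, proportions and listings show how many had the event, and the listings would allow a Kaplan-Meier re-analysis. All this stands and limits the severity, but it does not correct the tabulated median.

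Kaplan-Meier may add little with 3 to 6 ulcers. If 30% close, fewer than 3 of 6 close in 74% of studies, and the median is then not reached. When more close, the gap in a given sample can be small: with 4 of 6 closed at Days 60, 90, 120 and 180, the event-only median is 105 days and the Kaplan-Meier curve reaches 50% at Day 120. This too is fair. Still, not reached with 2/6 is a more accurate report than 75 days.

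Protocol 17.6 allows graphs where appropriate and Protocol 17.8 allows further exploratory and sensitivity analyses. These permit a better analysis, but the SAP plans none.

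On the minor point, Protocol 9.2.3.4 allows unscheduled visits with a skin/ulcer examination, so a two-week confirmation is possible.

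Three stronger readings are tempting. A reader might infer that the SAP expressly excludes patients without the event for all four endpoints; it does so only for closure. A reader might infer that the tables will conceal failures to heal; "The table shells can be found in a separate file", so labelling cannot be checked, and the planned incidences point the other way. A reader might infer that the rule always favours the drug; for new ulceration and recurrence it does the reverse.

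**Conclusion.** The point holds, at minor to moderate severity. A stated rule for closure, and an implied one for the other three endpoints, gives times that are conditional on the event and capped by follow-up. As times for all patients they are too short unless nearly all have the event. The closure medians differ by 120 days at 70% closing and by 210 days at 50% or 60%. Where fewer than half close, there is no Kaplan-Meier median to compare.

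The sizes rest on an assumed constant hazard, assumed event rates, visits on their nominal days and follow-up of all patients to Day 360. The direction does not depend on the exact model. A reader might also infer that unequal follow-up makes matters much worse. The documents do not establish this: Protocol 10.3 and 12.5 intend follow-up to continue after drug is stopped, and no dropout rate is given. The endpoints are exploratory, and the primary safety conclusion is unaffected.

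**What to change.** - In SAP 2.10.8, delete the sentence excluding ulcers that do not close.
- In SAP 2.10.1 and 2.10.8, report each time endpoint by Kaplan-Meier over all eligible patients, censored at the last assessment of that endpoint. State the assumption that dropout is unrelated to the outcome. Give events/N, number censored, and the median or a statement that it was not reached.
- Measure recurrence from the closure date, among patients whose ulcer closed.
- Label any event-only summary that is kept *among patients with the event, x/N*.
- Separately, reconcile the two wordings of the confirmation interval and state which visit dates closure. The confirming visit would fit closure incidence starting at Month 2 and recurrence at Month 3.

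The cost is SAP wording and a standard SAS procedure; no new data are needed. The downside is that with 3 to 6 ulcerated patients the median will often be not reached and intervals will be wide: for 2 of 6 closed, the exact 95% interval for the proportion is 4% to 78%.

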### Ulcer volume

Ulcer volume will be assessed using a 3D-imaging system. Data for ulcer volume will be provided to Integrium by an external vendor. Continuous outcome for volume and changes from baseline (Visit 2/Day 0) will be listed and summarized by descriptive statistics (n, mean, median, standard deviation, minimum and maximum).

The outcomes detailed below will be listed and summarized by descriptive statistics (n, mean, median, standard deviation, minimum and maximum) by visit.

- Incidence of new ulceration (defined as a site with no previous ulceration) at Months 1, 2, 3, 4, 5, 6, 9, and 12.
- Time to new ulceration defined as the difference between the date the new ulceration is reported and the date of first dose administration.

The outcomes detailed below will be listed and summarized by descriptive statistics (n, mean, median, standard deviation, minimum and maximum) by visit, separately for patients with ulceration at Baseline only.

- Incidence of complete wound closure of reference ulcer (defined as skin re-epithelialization without draining or dressing requirements confirmed at two consecutive study visits at least 2 weeks apart) at Months 2, 3, 4, 5, 6, 9, and 12.
- Time to complete wound closure of reference ulcer.
- Incidence of recurrence of reference ulcer after complete wound closure at Months 3, 4, 5, 6, 9, and 12.
- Time to recurrence of reference ulcer after complete wound closure.
- Change from Baseline in reference ulcer volume based on 3D scanning at Months 1, 2, 3, 4, 5, 6, 9, and 12.

